5.4.2.1. Management of Dose-Limiting Toxicities or Other Urgent Situations

In all cases, investigators may employ any measures or concomitant medications, after discussion with the sponsor (whenever possible), necessary to optimally treat the subject.

5.4.2.2. Follow-Up of Dose-Limiting Toxicities

Any DLT should be followed until it resolves to baseline or appears to have stabilized for a minimum of 30 days. During follow-up, subjects should be seen as often as medically indicated to assure safety.

5.4.3. Procedures for Cohort Review and Dose Escalation

Regular telephone conferences will be scheduled by the sponsor with study investigators in order to review cohort-specific data and overall safety data, to agree on dose escalation, adjudicate individual high-grade AEs as potentially dose-limiting, and guide other major study decisions.

5.4.4. Criteria and Procedures for Dose Interruptions and Adjustments of Study Treatment

General guidelines for management of toxicities are provided in [Table 9](#). Study treatment may be delayed up to 4 weeks (28 days) to allow for resolution of toxicity. If a dose interruption is necessary, all study treatment components should be interrupted.

Subjects may resume treatment if no medical condition or other circumstance exists that, in the opinion of the investigator, would make further participation in the study unsuitable. The treating investigator should contact the sponsor to discuss the case of any subject whose treatment has been delayed for more than 4 weeks (28 days) before restarting treatment with the study drugs.

Individual decisions regarding dose interruption or reduction should be made using clinical judgment and in consultation with the sponsor's medical monitor, taking into account relatedness of the AE to the study drug and the subject's underlying condition. Adverse events that have a clear alternative explanation or transient (≤ 72 hours) abnormal laboratory values without associated clinically significant signs or symptoms may be exempt from dose-reduction rules.

Dose interruptions are permitted in the case of medical/surgical events or logistical reasons not related to study therapy (eg, elective surgery, unrelated medical events, subject vacation, and/or holidays). Subjects should be placed back on study therapy within 4 weeks (28 days) of the scheduled interruption, unless otherwise discussed with the medical monitor. The reason for interruption should be documented in the subject's study record.

5.4.4.1. Epacadostat Dose Modifications

[Table 8](#) describes epacadostat dose reductions that may occur due to any related AEs. Dose reductions should occur in a step-wise fashion from the initial starting dose of the cohort, and a maximum of 2 dose reductions of epacadostat are allowed for the management of an AE. If an AE recurs/does not return to baseline after the second dose reduction of epacadostat, then the subject must permanently discontinue epacadostat.

The lowest permissible dose of epacadostat is 25 mg BID. If a subject does not tolerate 25 mg BID, then the subject must permanently discontinue epacadostat. If epacadostat is discontinued after 2 dose reductions, or if a 25 mg BID dose is not tolerated, the subject may resume treatment with nivolumab monotherapy (or nivolumab with ipilimumab, if applicable) once criteria for restarting study treatment have been met with approval from the medical monitor.

Table 8: Dose Reductions of Epacadostat (Treatment Groups A and B)

Dose of Epacadostat	Dose Level -1	Dose Level -2
	First Reduction of Epacadostat	Second Reduction of Epacadostat
100 mg BID	50 mg BID	25 mg BID
50 mg BID	25 mg BID	N/A – Discontinue Treatment
25 mg BID	N/A – Discontinue Treatment	N/A – Discontinue Treatment

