5.2. Study Drugs

5.2.1. Epacadostat

For all subjects, epacadostat will be self-administered beginning on Cycle 1 Day 1 and continuously thereafter. Doses will be taken BID, in the morning and evening, approximately 12 hours apart without regard to food. If a dose is missed by more than 4 hours, then that dose should be skipped and the next dose should be taken at the next scheduled timepoint.

On Cycle 1 Day 1, Cycle 1 Day 8, and Cycle 2 Day 1, the morning dose of epacadostat will be administered at the study site, as these study visits coincide [REDACTED]. On visit days when nivolumab and ipilimumab (Treatment Group A) or nivolumab and lirilumab (Treatment Group B) are administered, epacadostat should be taken before the start of any infusions.

Note: Subjects who are ongoing on study treatment as of the date of Amendment 2 may discontinue epacadostat at the discretion of the treating investigator (see Section 1.7).

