5.4.8. Criteria for Permanent Discontinuation of Study Treatment

The occurrence of unacceptable toxicity not caused by the underlying malignancy will be presumed to be related to study treatment and will require that the study drug be permanently discontinued. Unacceptable toxicity is defined as follows:

- Grade 4 or life-threatening AEs, except with approval from the medical monitor.
- Toxicity requiring more than 2 dose reductions of epacadostat, or dose reductions below 25 mg BID.
- \geq Grade 2 ocular irAE.
- Occurrence of an AE that is related to treatment with the study drug that, in the judgment of the investigator or the sponsor's medical monitor, compromises the subject's ability to continue study-specific procedures or is considered to not be in the subject's best interest.
- Persistent AE requiring a delay of therapy for more than 4 weeks (28 days) unless a greater delay has been approved by the sponsor.

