5.5. Withdrawal of Subjects From Study Treatment

5.5.1. Withdrawal Criteria

Subjects may withdraw consent at any time for any reason or be withdrawn from study treatment at the discretion of the investigator should any untoward effect occur. In addition, a subject may be withdrawn by the investigator or the sponsor if enrollment in the study is inappropriate, the study plan is violated, or for administrative and/or other safety reasons.

Subjects **must** be withdrawn from study treatment for the following reasons:

- The subject becomes pregnant.
- Consent is withdrawn. Subjects may choose to withdraw from the study at any time without penalty of jeopardizing their health care or loss of benefits to which the subject is otherwise entitled.
Note: Consent withdrawn means that the subject can no longer be followed and no additional data can be collected.
- Further participation would be injurious to the subject's health or well-being, in the investigator's medical judgment.
- Unacceptable toxicity (see Section 5.4.8). Subjects with unacceptable toxicities must be withdrawn from study treatment but will continue in the safety follow-up period of the study (see Section 6.4).
- The subject has received study treatment for 2 years (ie, 24 months have elapsed since Cycle 1 Day 1).
- The study is terminated by the sponsor.
- The study is terminated by the local health authority, IRB, or IEC.

A subject **may** be discontinued from study treatment as follows:

- Radiographic progression of disease per RECIST v1.1 (see [Appendix E](#)). A subject may continue on treatment after radiographic progression is confirmed per RECIST v1.1 if clinically stable or clinically improved, pending confirmation of disease progression [REDACTED] (see Sections [5.5.1.1](#) and [7.6.1](#)).
- If, during the course of the study, a subject is found not to have met eligibility criteria (see Section [3](#)), the medical monitor, in collaboration with the investigator, will determine whether the subject should be withdrawn from the study.
- If a subject is lost to follow-up or noncompliant with study procedures or study treatment in the investigator's opinion, the sponsor should be consulted for instruction on handling the subject.

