5.5.2. Withdrawal Procedures

In the event that the decision is made to permanently discontinue the study drug, the subject will be withdrawn from the study and the EOT visit should be conducted. Reasonable efforts should be made to have the subject return for the safety follow-up visit (see Section 6.4). The last date of the last dose of study drug and the reason for subject withdrawal will be recorded in the eCRF.

If a subject is withdrawn from all study treatment:

- The study monitor or sponsor must be notified.
- The reason(s) for withdrawal must be documented in the subject's medical record and in the eCRF.

Note: The reason for withdrawal from treatment may be different than the reason for withdrawal from study.

- The EOT visit should be performed.
- The date of the EOT visit should be recorded in the eCRF and IRT.
- Subjects must be followed for safety until the time of the follow-up visit or until study drug–related toxicities resolve, return to baseline, or are deemed irreversible, or until the subject begins new anticancer therapy, whichever is longest.

If the subject discontinues study treatment and actively withdraws consent for collection of follow-up data (safety follow-up), then no additional data collection should occur; however, subjects will have the option of withdrawing consent for study treatment but continuing in the safety follow-up period.

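### When epacadostat 25 mg BID is not tolerated, section 5.4.4.1 lets the antibodies resume with medical monitor approval, but 5.4.8 read with 5.5.1 requires withdrawal from study treatment

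*Combined protocol and SAP*

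**What the plan says.** **Continuing the antibodies.** Section 5.4.4.1 sets the condition, "If epacadostat is discontinued after 2 dose reductions, or if a 25 mg BID dose is not tolerated", and the consequence, "the subject may resume treatment with nivolumab monotherapy (or nivolumab with ipilimumab, if applicable"). The same sentence adds that restart criteria must be met and that the medical monitor must approve. Table 8, in the same section, gives "N/A – Discontinue Treatment" where no further epacadostat reduction is available.

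**Stopping.** Section 5.4.8, whose heading concerns permanent discontinuation of study treatment, lists as unacceptable toxicity: "Toxicity requiring more than 2 dose reductions of epacadostat, or dose reductions below 25 mg BID". Its consequence is permanent discontinuation of *the study drug*, in the singular and undefined. Section 5.5.1 refers to 5.4.8 and, in its list of mandatory reasons, says: "Subjects with unacceptable toxicities must be withdrawn from study treatment but will continue in the safety follow-up period of the study".

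**Related wording.** Section 5.5.2 says: "In the event that the decision is made to permanently discontinue the study drug, the subject will be withdrawn from the study", and calls for the EOT visit. The synopsis paragraph on imaging drops the imaging requirement once *study drug* is discontinued. In contrast, section 6.3 ties the EOT visit to stopping all components, and 7.6.3 ends imaging when all study treatment stops (or at another listed event). Two further places foresee stopping epacadostat alone. Section 5.4.6 does so after certain cases of serotonin syndrome. The Amendment 2 note in 5.2.1 says that ongoing subjects "may discontinue epacadostat at the discretion of the treating investigator".

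**The concern.** A subject who cannot tolerate the lowest epacadostat dose should meet one rule. Here one section allows the antibodies to resume under a stated control, and another pair of sections ends study treatment without one. Several data points follow from the choice:

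- the date treatment ends and the EOT visit;
- the last required scan, and with it the follow-up behind progression-free survival (PFS) and duration of response (DOR);
- the 30-day and 100-day safety visits, which section 6.4.1 times from the EOT visit, and the adverse event reporting period of at least 100 days, which runs from the last dose of study treatment.

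Subjects with the same toxicity history could be handled differently, and the difference would come from the text and not from a clinical judgement.

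**Working it through.** No sample size, power or error rate is involved, so the check compares trigger and consequence across sections.

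**Step 1: do the triggers coincide?** Inputs are the Table 8 reductions and the 25 mg BID floor in 5.4.4.1.

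| Epacadostat starting dose | Reductions available | Step after 25 mg BID fails | Meets 5.4.4.1 | Meets the 5.4.8 dose-reduction item |
|---|---|---|---|---|
| 100 mg BID | 100 to 50 to 25 (two) | third reduction, below 25 mg BID | yes, on both conditions | yes, on both limbs |
| 50 mg BID | 50 to 25 (one) | second reduction, below 25 mg BID | yes, 25 mg BID not tolerated | yes, below 25 mg BID |
| 25 mg BID | none | first reduction, below 25 mg BID | yes, 25 mg BID not tolerated | yes, below 25 mg BID |

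In every row, the subject who may resume the antibodies under 5.4.4.1 also has unacceptable toxicity under 5.4.8.

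**Step 2: are the consequences compatible?** Section 5.4.4.1 permits resumption with approval. Section 5.5.1 requires withdrawal from *study treatment*, and section 5.4.1 lists the components of that term as epacadostat, nivolumab, and ipilimumab or lirilumab. The consequences are opposite.

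**Step 3: is there an exception that joins them?** Section 5.4.8 has five items. Two carry an approval route: the Grade 4 or life-threatening item (medical monitor) and the prolonged-delay item (sponsor). The dose-reduction item carries none.

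**Step 4: does a reading of *the study drug* remove the conflict?**

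- *Epacadostat only.* Section 5.4.8 taken alone then agrees with 5.4.4.1. Section 5.5.1 does not, because it says *study treatment*. Section 5.5.2, read literally, would also withdraw from the study a subject who stops epacadostat alone, against 5.4.4.1, 5.4.6 and the Amendment 2 note.
- *All components.* Section 5.5.2 then fits 6.3 on the EOT visit, but 5.4.8 contradicts 5.4.4.1 directly.

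Neither reading makes all the sections agree. Table 8 has the same ambiguity, since its entry says treatment and does not name epacadostat.

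**The case against.** The best defence is that a specific, controlled provision governs over general withdrawal wording. Resumption under 5.4.4.1 is case by case and needs medical monitor approval, so a site does not choose alone. The item in 5.4.8 concerns epacadostat reductions, Table 8 is titled for epacadostat, and elsewhere the protocol often says *all study treatment* when it means every component. An epacadostat-only reading of 5.4.8 is therefore plausible. Section 5.5.1 also takes its scope from 5.4.8 by cross-reference. Once continuation is approved, 6.3, 6.4.1 and 7.6.3 settle the EOT visit, safety follow-up and imaging.

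Much of this stands as evidence of intent. It does not cure the text. Section 5.5.1 uses mandatory language and the wider term, the heading of 5.4.8 uses the wider term too, and a footnote to Table 9 sends readers handling epacadostat reductions to 5.4.8 for study treatment withdrawal criteria. No section says that 5.4.4.1 takes precedence.

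A reader might infer from 5.5.2 that every subject who stops epacadostat under Amendment 2 must leave the study. The documents do not support that. Appendix F gives as a purpose of the amendment that epacadostat may stop while nivolumab and ipilimumab continue. That stop is discretionary, so 5.4.8 and the toxicity rule in 5.5.1 are not engaged. Within 5.5.2, the action list is introduced for withdrawal from all study treatment, and the section still asks for safety follow-up. The 5.5.2 sentence is loose wording and a secondary point.

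**Conclusion.** The contradiction between 5.4.4.1 and 5.4.8 with 5.5.1 is established on the current text and does not depend on how *the study drug* is read. The wording in 5.5.2 and the synopsis adds to it but would not carry the point alone.

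For any subject it reaches, the conflict decides whether antibody treatment continues. Across the trial its effect is limited. The documents give no count of ongoing subjects or of subjects at or near intolerance of 25 mg BID. Enrollment is closed, Treatment Group B enrolled nobody, and section 9.4 replaces efficacy summary tables with listings. No summary result is shown to change.

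A reader might take the remainder of the 2-year treatment period as the size of the discrepancy. That is only a ceiling for one subject. Nothing in the documents shows how long such a subject would otherwise stay on the antibodies. The point warrants correction because the rule still governs ongoing subjects. It does not show that the analysis is compromised.

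**What to change.** - Reconcile 5.4.4.1 and Table 8 with 5.4.8 and 5.5.1.
- For each item in 5.4.8, state whether it ends epacadostat only or all study treatment, and whether the medical monitor condition in 5.4.4.1 applies to it.
- In 5.4.8, 5.5.2 and the synopsis sentence on imaging, replace *study drug* with either *epacadostat* or *all study treatment*, so that these places agree with the EOT rule in 6.3 and the imaging rule in 7.6.3.
- In 5.5.2, separate withdrawal from treatment from withdrawal from the study.

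The sponsor decides which clinical rule applies. This review only asks that the sections state the same one.

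The cost is wording in a protocol amendment, with the usual sponsor and IRB/IEC approval, and no added visits or data collection.

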5.4.4.2. Nivolumab, Ipilimumab, and Lirilumab Dose Modifications

There will be no dose reductions of nivolumab, ipilimumab, or lirilumab allowed for the management of toxicities of individual subjects. Doses of these agents are held for toxicity management, per Table 9. See Section 5.4.5 for dose modification and toxicity management guidelines pertaining to specific irAEs.

Table 9: General Guidelines for Interruption and Restarting of Study Treatment

CTCAE Grade/Severity	Hold Treatment (Y/N)	Timing for Restarting Treatment	Dose Level for Restarting Epacadostat	Dose Level for Restarting Nivolumab and Ipilimumab (Treatment Group A), or Nivolumab and Lirilumab (Treatment Group B)	Treatment Discontinuation
1-2 (Mild-moderate)	No	Continue treatment at the discretion of the investigator.	N/A – If held, restart at same dose.	NA - If held, restart at same dose.	N/A
3 ^a (Severe)	Yes	Toxicity resolves to Grade 0-1.	Reduce by 1 dose level. ^b	Restart same dose.	Toxicity does not resolve within 4 weeks (28 days) of last dose, except by approval of the medical monitor. OR Second occurrence of previously resolved Grade 3 AE.
4 ^c (Life-threatening)	Yes	Permanent discontinuation, except by approval of the medical monitor. If continuing, toxicity must resolve to Grade 0-1.	Permanent discontinuation, except by approval of the medical monitor. If continuing, reduce by 1 dose level. ^b	Permanent discontinuation, except by approval of the medical monitor. ^c If continuing, restart same dose.	Permanent discontinuation for any severe or life-threatening event, except by approval of the medical monitor.

^a Grade 3 amylase or lipase abnormalities that are not associated with symptoms or clinical manifestations of pancreatitis do not require a dose delay. It is recommended to consult with the medical monitor for Grade 3 amylase or lipase abnormalities.

^b See Table 8 for epacadostat dose reduction guidelines. See Section 5.4.8 for study treatment withdrawal criteria.

^c Isolated Grade 4 lipase or amylase abnormalities not associated with symptoms or clinical manifestations of pancreatitis may not require treatment discontinuation. Medical monitor should be consulted for any Grade 4 amylase or lipase abnormality.

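### For a subject who started epacadostat at 100 mg BID, Table 9 ends treatment at a second Grade 3 occurrence while Section 5.4.4.1 and Table 8 still allow a second reduction, and no text says which governs

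*Combined protocol and SAP*

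**What the plan says.** Three places in the protocol govern what happens after a severe AE.

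- **Section 5.4.4.2, Table 9, Grade 3 row.** Treatment is held until the event is Grade 0 or 1. The instruction for restarting epacadostat is "Reduce by 1 dose level", and the antibodies restart unchanged. The discontinuation column gives two grounds joined by OR: failure to resolve within 4 weeks, with a medical monitor exception, and "Second occurrence of previously resolved Grade 3 AE", with no exception attached. The footnote on the dose-level instruction reads "See Table 8 for epacadostat dose reduction guidelines. See Section 5.4.8 for study treatment withdrawal criteria".
- **Section 5.4.4.1 and Table 8.** The text says that Table 8 "describes epacadostat dose reductions that may occur due to any related AEs" and that "a maximum of 2 dose reductions of epacadostat are allowed for the management of an AE". It then adds its own recurrence rule: "If an AE recurs/does not return to baseline after the second dose reduction of epacadostat, then the subject must permanently discontinue epacadostat". For a subject who starts at the highest dose, the Table 8 sequence is "100 mg BID 50 mg BID 25 mg BID". For a 50 mg BID start, Table 8 has one reduction and then discontinuation; for 25 mg BID it has none. If epacadostat is stopped after two reductions, or 25 mg BID is not tolerated, nivolumab with or without ipilimumab may resume once the restart criteria are met and the medical monitor approves.
- **Section 5.4.8.** The criterion on reductions is "Toxicity requiring more than 2 dose reductions of epacadostat, or dose reductions below 25 mg BID". The list contains no criterion for a second Grade 3 occurrence.

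**The concern.** Table 9 and Section 5.4.4.1 each contain a recurrence rule, and they place it at different points. Table 9 attaches discontinuation to the second Grade 3 occurrence, when one reduction has been used. Section 5.4.4.1 attaches the mandatory stop of epacadostat to recurrence after two reductions. The Table 9 footnote sends the reader to Table 8 and Section 5.4.8, and neither mentions the second-occurrence ground.

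Two sites could therefore manage the same recurrent severe toxicity differently and both cite the protocol. That matters first for subjects still on treatment in Treatment Group A. It also matters for interpreting the safety data: safety and tolerability are the Phase 1 primary objective, and Section 5.4.2 allows a lower MTD to be set on toxicity seen after the DLT window. Whether a subject appears as an AE discontinuation or as a second dose reduction would depend on the rule the site followed.

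**Working it through.** No sample size, power or error rate bears on this point, so the check is a trace of both rules.

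**Scenario.** A related Grade 3 AE resolves to Grade 0 or 1, epacadostat restarts one level lower, and the same AE recurs at Grade 3.

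| Starting dose | Dose at recurrence | Table 9 | Section 5.4.4.1 and Table 8 | Result |
|---|---|---|---|---|
| 100 mg BID | 50 mg BID | Discontinue treatment | Second reduction to 25 mg BID allowed | Diverge on epacadostat and on the whole regimen |
| 50 mg BID | 25 mg BID | Discontinue treatment | No second reduction; epacadostat stops, antibodies may resume with approval | Agree on epacadostat; unclear on the antibodies |
| 25 mg BID | Not applicable | Not applicable | No first reduction exists | Scenario cannot arise |

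The divergence on epacadostat therefore occurs at 1 of the 3 doses in Table 8. Section 4.1.1 sets 50 mg BID as the Phase 1 starting dose, with 100 mg BID as Dose Level 2.

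**Size of the gap from 100 mg BID.** With one reduction after each episode that does not end treatment, reductions used at the stop equal episodes minus 1. Table 9 stops at episode 2, so 2 − 1 = 1 reduction. If the second reduction is taken, Section 5.4.4.1 requires epacadostat to stop at episode 3, so 3 − 1 = 2 reductions. The gap is one step.

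**Which events are left.** Section 5.4.4.2 refers specific irAEs to Section 5.4.5.

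- Grade 3 pneumonitis, enterocolitis, hepatitis and neuropathy discontinue at the first occurrence unless the medical monitor approves an exception (Tables 11, 12, 13 and 15).
- Grade 3 dermatitis and endocrinopathy have their own restart rules, including restart at the same dose (Tables 14 and 16).
- Other severe immune-mediated reactions are stopped permanently (Section 5.4.5.7).

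What remains is mainly related, non-immune Grade 3 AEs.

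**Is there a tie-breaker?** None was found. The Table 9 footnote points to Table 8 and Section 5.4.8 without ranking them. Section 5.4.4 calls Table 9 general guidelines and asks for clinical judgment and medical monitor consultation, but that sentence concerns interruption or reduction, not discontinuation.

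**The case against.** The strongest answer is that the rules can be followed together. Section 5.4.4.1 is permissive: it says that reductions may occur, sets a maximum, and names one condition under which epacadostat must stop. It does not say that this is the only such condition. Table 9 is split by grade and Section 5.4.4.1 is not, so Table 9 can be read as a narrower Grade 3 rule operating beneath a grade-free cap. A site that stops at the second Grade 3 occurrence breaches nothing in Section 5.4.4.1 or 5.4.8. Nor does this reading make the second step in Table 8 redundant. It can still be reached through a different Grade 3 AE, a Grade 4 AE continued with approval, or a Grade 2 irAE that is slow to resolve.

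Much of this stands. A reader might infer that the protocol orders opposite actions for any subject with a recurrent Grade 3 AE, or that Table 9 makes the second reduction unreachable. The documents support neither: the second reduction is allowed rather than directed, it exists only from 100 mg BID, and it has other routes.

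What does not stand is that the matter is therefore settled. The cap-with-exception reading is reasonable but written nowhere. Section 5.4.4.1 has a recurrence rule of its own, worded for any AE, and nothing confines it to the other routes. The silence of Section 5.4.8 is only weak evidence, because that list has a catch-all for AEs judged contrary to the subject's interest and other stopping rules also lie outside it. It does mean, however, that following the footnote gives the reader no answer.

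**Conclusion.** The inconsistency is real and narrow. It affects a subject who started at 100 mg BID and has a related Grade 3 AE, outside the specific rules of Section 5.4.5, that resolves and recurs at Grade 3 after one reduction. Its size is one reduction step, and it also decides whether the whole regimen stops. For a 50 mg BID starter the only open question is resumption of the antibodies: Section 5.4.4.1 allows it with approval, while the Table 9 column refers to discontinuing treatment without separating the components.

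The documents do not say how many subjects are affected, or whether anyone started at 100 mg BID. Impact is limited: enrollment is closed, Treatment Group B enrolled no one, ongoing subjects may stop epacadostat at the investigator's discretion, and Section 9.4 restricts the analyses.

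A reader might also infer that the planned irAE summary in Section 9.4.2.5 is distorted. That is not shown. Most specified irAEs fall outside the scenario, and if interruption, reduction and discontinuation are counted as one item, a held irAE is counted under either rule. The point rests on the wording alone and takes no position on which clinical rule is right.

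**What to change.** Reconcile Table 9, Section 5.4.4.1 with Table 8, and Section 5.4.8 in one statement, repeated consistently in all three places. It should say:

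- how the second-occurrence ground in Table 9 interacts with the two-reduction allowance;
- whether discontinuation in that cell means epacadostat alone or all components, and so whether the antibodies may resume;
- whether the medical monitor exception extends to that ground.

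Which rule applies is for the sponsor to decide. In the disposition and dose-modification listings, identify any subject already managed under either reading, so that stops and reductions can be interpreted.

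The cost is a wording change in two sections and one table cell, by amendment or clarification letter, plus a check of existing records. It needs no new data collection and no further subjects.
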